6.18. Safety Contact Information

Contact information for AE reporting may be found in a separate Study Reference Manual and Study Safety Plan. Site personnel may also contact the medical monitor for any safety concerns or questions.

6.19. Definition of Clinical Significance

A change in a subject's clinical status is regarded as important, whether or not it is due to an intervention in the context of a clinical study. The assessment of whether a result is clinically significant or not will be made, taking into account: a) whether the result is out of expected

values documented by laboratory reference ranges, and this is true after the assessment has been repeated, b) other symptoms being exhibited by the study subject and medical history and c) the opinion of the treating physician.

6.20. Study Stopping Rules

CTCAE, version V5, 27Nov2017 criteria will be used during this study (Refer also to [Section 6.17.3](#)).

The study will be discontinued for any of the following:

- Using CTCAE criteria, the study will be stopped for review if drug-related toxicities of Grade 3 or greater (or a SAE) are observed in 2 or more subjects on active treatment in that dose group.
- If any unacceptable safety findings are identified at any time during the study and/or if ≥ 1 subject experience a related SAE or a related significant AE that, in the opinion of the CRC, warrants discontinuation of the study.
- Any other safety concern based on the judgment of the PI and/or medical monitor and reviewed by the CRC.

If post dosing EEG's demonstrate evidence of epileptiform abnormalities, in any subject as evaluated by an epileptologist or a Level 3 ANZAN certified neurologist, all dosing will be suspended pending review and approval by the CRC.

The decision to stop the study will be made by the CRC. Refer to [Section 9.8](#) for additional information on the CRC.

6.20.1. Maximum Clinical Exposure

Clinical PK will be considered as criteria for escalation of clinical doses. Dosing will not exceed $1/10^{\text{th}}$ of the exposure associated with the NOEL of 2.75 mg/kg observed in the 14-day dog EEG study (KNX100 C_{max} and $AUC_{0-\text{last}}$ of 84.9 ng/mL and 82.7 hr \times ng/mL, respectively and KNX100A C_{max} and $AUC_{0-\text{last}}$ of 26.5 ng/mL and 45.7 hr \times ng/mL, respectively).

6.20.2. Maximum Tolerated Dose Definition

The maximum tolerated dose (MTD) is defined as the dose below a non-tolerated dose and therefore can only be determined by the observation of a dose level, which is no longer considered acceptable in healthy subjects.

In this study, a dose will be considered non-tolerated and dose escalation will cease if 2 or more subjects in a cohort experience an AE of Grade 3 or higher occurring within 48 hours of administration of KNX100 or placebo at the dose level. Once the non-tolerated dose is defined,

the MTD will be confirmed at the previous dose level below the non-tolerated dose, or a dose between the non-tolerated dose and the last tolerated dose may be investigated. If the dose-escalation scheme is successfully completed for all escalating doses, 35 mg/day will be the highest dose studied (refer to [Section 5.3.2](#) and [Section 5.3.3](#) for the dosing schedule).

6.21. Removal of Subjects from the Study or Study Drug

6.21.1. Criteria for Discontinuation or Withdrawal of a Subject

The primary reason for discontinuation or withdrawal of the subject from the study should be recorded in the eCRF, using the following categories:

- Voluntary withdrawal by subject decision
 - The subject is at any time free to withdraw his or her participation in the study, without prejudice and independent of any decision concerning participation in other aspects of this study.
- AE
 - The subject has experienced an AE that requires early termination because continued participation imposes an unacceptable risk to the subject's health, or the subject is unwilling to continue because of the AE.
- Vital signs
 - Measurement of abnormal and out of range parameters on repeat analysis as required (postdose):
 - O₂ saturation of <90% for 60 seconds or longer
 - Respiratory rate of <8 breaths/minute for 2 or more minutes
 - Heart rate of <50 bpm
 - Systolic blood pressure of ≤80 mmHg
 - Temperature of ≤32°C
- EEG
 - Evidence of the emergence of epileptiform discharges as evaluated by an epileptologist or a Level 3 ANZAN certified neurologist.
- ECG
 - QTcF duration >475 ms and increase exceeding 40 ms in males
 - QTcF duration >475 ms and increase exceeding 60 ms in females
- Thyroid function tests outside the normal reference ranges (and upon repeat) and CTCAE Grade 2 or above. That is, symptomatic and requiring treatment.
- Laboratory Parameters
 - Safety laboratory tests that are outside the normal reference ranges (and upon repeat) and deemed clinically significant by the study PI.

- Pretreatment event
 - The subject has a pretreatment event that requires early termination because continued participation imposes an unacceptable risk, or the subject is unwilling to continue due to the pretreatment event.
- Pregnancy
 - If the subject is found to be pregnant, the subject must be withdrawn immediately.
- Major protocol deviation as judged by the investigator and/or Kinosis.
 - The discovery post-randomization that the subject was incorrectly initiated on investigational drug, failed to meet protocol entry criteria, or did not adhere to protocol requirements **and** continued participation poses an unacceptable risk to the subject's health.
- Compliance
 - The subject has poor compliance with study drug or study procedures.
- Additional treatment
 - The subject requires treatment with another drug that will interfere with evaluation of the study drug.

Subjects that are withdrawn from the study but are evaluable will not be replaced. Any subject that is withdrawn and is not evaluable will be replaced to ensure a minimum number of evaluable subjects.

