4.3. Exclusion Criteria

Subjects will **not** be eligible for participation in the study if they meet ANY of the following exclusion criteria.

1. Clinically significant history or presence of significant cardiovascular, respiratory, hepatic, renal, gastrointestinal, endocrinological, hematological, neurological, or psychiatric disorder. Any surgical or medical history which may significantly alter the absorption, metabolism, or elimination of drugs or constitute a risk when taking the study intervention; or interfering with the interpretation of data (e.g., gastric bypass, cyclical vomiting, etc.). This includes a history of lymphoma, leukemia, or any malignancy within 5 years except for basal cell or squamous epithelial carcinomas of the skin that have been resected with no evidence of metastatic disease for 3 years.
2. Subjects who have a sitting or semi-supine blood pressure at screening or Day-1, after resting for at least 3 minutes of systolic blood pressure >140 or <100 mmHg, or diastolic blood pressure >90 or <60 mmHg.
3. Subjects who have a sitting or semi-supine pulse rate at screening or Day-1, after resting for at least 3 minutes, outside the range of <50 or >90 beats/minute
4. Subjects who donated blood or who had a comparable blood loss (approximately 500 mL) during the last 30 days prior to start of this study and while on study.
5. Clinically significant findings on the screening, Day -1, or predose Day 1 electrocardiogram (ECG) or physical examination, including QTcF duration >450 ms for males and >470 ms for females on ECG.
6. Thyroid function tests outside the normal reference ranges and deemed clinically significant by the study PI (and upon repeat).

7. Safety laboratory tests that are outside the normal reference ranges and deemed clinically significant by the study PI (and upon repeat).
8. Any history of meningitis, septicemia, or pneumonia.
9. Any history or family history (first or second degree relative) of seizure disorder, febrile convulsions.
10. Any clinically significant medical history of closed head trauma.
11. Any history of anaphylaxis or other significant allergy.
12. Any current diagnosis or clinically significant medical history of psychiatric illness as diagnosed and documented by a medical practitioner and as defined by the American Psychiatric Association Diagnostic and statistical manual of mental disorders 5th edition (DSM-5).

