- Nonhormonal intrauterine device (IUD)
- Bilateral tubal occlusion
- Vasectomized subject/partner with documented azoospermia 90 days after procedure if that partner is the sole sexual partner.

For female participants, hormonal contraceptives should begin at least 1 month prior to screening to ensure contraceptive is in full effect.

Complete abstinence, defined as the complete avoidance of heterosexual intercourse, is an acceptable form of contraception if used consistently throughout the duration of study and for the durations after dosing specified for males and females above. It is not necessary to use any other method of contraception when complete abstinence is elected. WOCBP who choose complete abstinence must continue to have pregnancy tests as per protocol. The reliability of sexual abstinence needs to be evaluated by the investigator in relation to the duration of the clinical study and the preferred and usual lifestyle of the subject.

6.10. 12-Lead Electrocardiograms

12-lead ECGs will be used to evaluate heart rate, atrial ventricular conduction, QRS and QT intervals, and possible arrhythmias. ECGs include ventricular heart rate; QRS duration; PR, RR, QT, QTcB, and QTcF intervals; and P and T wave. Evaluations will be recorded as normal, abnormal (not clinically significant), or abnormal (clinically significant).

The 12-lead ECGs will be obtained after the subject has been resting semi-supine for at least 3 minutes prior to the indicated times. All ECGs should be recorded with the subject in the same physical position. For each time point, 3 ECG recordings should be taken at approximately 1 to 3-minute intervals.

A standardized ECG machine should be used, and the subject should be tested using the same machine throughout the study, if possible. When the timing of these measurements coincides

with a blood collection, obtain the ECG prior to the nominal time of the blood collection, blood pressure, and heart rate.

Additional ECGs should also be collected if a subject experiences a cardiac AE.

After ECGs have been recorded, the PI or a designated physician will review each of the ECGs. If available, a paper copy should be filed in the subject's medical records. For all ECGs, ECG intervals and an overall assessment will be recorded. Evaluations will be recorded as normal, abnormal (not clinically significant), or abnormal (clinically significant).

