6.17. Adverse Events Assessments

Any new event or experience that was not present at Screening, or the worsening of an event present at Screening, is considered an AE ([Section 6.17.1](#)). The investigator is responsible for following all AEs from onset to adequate resolution (event is resolved or subject is medically stable), where possible ([Section 6.17.8](#)).

AEs will be documented from physical or neurological examination findings, clinically significant laboratory results (as per reference ranges indicated in the Study Procedures and Laboratory Manuals), vital signs, ECGs, EEGs, or any other assessments that are relevant to subject safety.

The PI is responsible for reporting of all safety events that occur within the AE reporting period and will classify severity ([Section 6.17.3](#)) and relationship to study drug ([Section 6.17.4](#)) for each event. Any event that meets the definition of a serious adverse event (SAE; [Section 6.17.10](#)) will be recorded and reported as an SAE.

The PI or designee is responsible for recording all AEs on the appropriate study specific CRF, regardless of the AE's likely relationship to study treatment. Any changes in severity of an AE will be recorded and any AEs characterized as intermittent will be documented for each episode.

The CRF has been designed to capture the data elements recommended for reporting of drug safety events under current International Conference on Harmonisation (ICH) guidelines (ICH E2A, E6).

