6.17.9. Clinical Laboratory and Investigational Findings Adverse Events

Abnormal laboratory findings and other abnormal investigational findings (for example, on an ECG trace) should not be reported as AEs unless they are associated with clinical signs and symptoms, lead to treatment discontinuation, or are considered otherwise medically important by the investigator. If a laboratory abnormality fulfills these criteria, the identified medical condition (i.e., anemia, increased alanine aminotransferase [ALT]) must be reported as the AE rather than the abnormal value itself.

The investigator must review the laboratory report, document this review, and record any clinically relevant changes occurring during the study in the AE section of the CRF. The laboratory reports must be filed with the source documents. Clinically significant abnormal laboratory findings are those which are not associated with an underlying disease, unless judged by the investigator to be more severe than expected for the subject's condition.

All laboratory tests with values considered clinically significantly abnormal during participation in the study or within 1 day after the last dose of study drug should be repeated until the values return to normal (or baseline) or are no longer considered clinically significant by the investigator or medical monitor. If such values do not return to normal/baseline within a period of time judged reasonable by the investigator, the etiology should be identified, and the Sponsor notified.

All protocol-required laboratory assessments must be conducted in accordance with the laboratory manual and the SOA in [Appendix 1](#) and [Appendix 2](#). If laboratory values from non-protocol specified laboratory assessments performed at the institution's local laboratory require a change in subject management or are considered clinically significant by the investigator (e.g., SAE, AE, or dose modification), then the results must be recorded in the CRF.

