Appendix 4 KTX-101 Normal Ranges for Vital Signs and ECG Parameters**VITAL SIGNS**

Parameter	Normal Range	Units
Pulse Rate	50 – 100	beats per minute (bpm)
Systolic Blood Pressure	90 - 140	mm Hg
Diastolic Blood Pressure	40 - 90	mm Hg
Respiratory Rate	10 - 22	respirations per minute
Oral Temperature	35.5 – 37.5	°C
Pulse Oximetry	≥ 95	%

ECG PARAMETERS

Parameter	Normal Range	Units
Heart Rate	50 – 100	bpm
PR Interval	≥ 120 to ≤ 220	msec
QRS Duration	< 120	msec
QT Interval	< 500	msec
QTcB	≤ 450 (both genders)	msec
QTcF	≤ 450 (both genders)	msec

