5.2 General Definitions

Variable	Definition
Study Day	
 • Study Day = date of interest – treatment start date + 1, when the date of interest \geq treatment start date; • otherwise, Study Day = date of interest – treatment start date. 
Note: if either date is missing, Study Day calculations will not be performed. Should imputation be performed, then Study Day may be computed, where appropriate.

Baseline	
For ECG data, baseline is defined as the average of up to three measurements taken at the pre-dose timepoint on the Day 1 Visit if available; otherwise, baseline is defined as the last single tracing measurement taken prior to the first dose of study treatment.
 
For EEG data, baseline is defined as the assessment collected at the Screening Visit (Day -2) in which the patient was in a sleep deprived state.
 
For all other endpoints, baseline is defined as the last non-missing value collected prior to receiving the first dose of study treatment (based on date and time of administration as applicable). For endpoints with both planned pre-dose and post-dose timepoint assessments on Day 1, only pre-dose assessments will be considered as a candidate for baseline. For MAD Cohort 3, vital signs

	assessments on Day 1 associated with the second dose (i.e., evening) will not be considered as a candidate for baseline.
Post-baseline	Defined as values collected after receipt of the first dose of study treatment (based on date and time of administration as applicable)
Change from Baseline	Defined as: Post-baseline value – Baseline value
Duration on Study (in days)	End of study date – randomization date + 1
BMI (kg/m ²)	BMI is collected in the clinical database
Age (yr)	Age is collected in the clinical database
Study Completion	Defined as attendance at the End of Study (EOS) Visit.

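### The QTcF withdrawal criterion for women has no absolute cap: with a baseline above 440 ms, QTcF can pass 500 ms (up to 530 ms) without meeting it

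*Protocol*

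**What the plan says.** Protocol 6.21.1 lists the grounds for withdrawing a subject. For women the ECG ground is "QTcF duration >475 ms and increase exceeding 60 ms in females". For men the level is the same and the required increase is more than 40 ms. No QTcF value is sufficient by itself for either sex.

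Entry is governed by Exclusion 5 in Protocol 4.3. It bars clinically significant ECG findings at screening, Day -1 or predose Day 1, "including QTcF duration >450 ms for males and >470 ms for females on ECG". Protocol Appendix 4 gives 450 ms as the upper end of normal QTcF for both sexes.

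The value 500 ms appears as the start of the highest QTc reporting band in Protocol 8.6 and SAP 6.4.5. It does not appear as a withdrawal or stopping limit.

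Protocol 6.21.1 does not say which ECG the increase is measured from. SAP 5.2 does define an ECG reference for the analysis: "baseline is defined as the average of up to three measurements taken at the pre-dose timepoint on the Day 1 Visit if available", and otherwise the last single tracing before the first dose.

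**The concern.** When a level and a rise must both be met, the stricter of the two decides. For a woman who enters with a long QTcF, the 475 ms level stops mattering and only the 60 ms rise counts. Women also have the higher entry limit and the larger permitted rise, and the two combine. A woman could then be in the plan's highest QTc band and still not meet the written withdrawal rule.

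This is of consequence in Part B. Dosing there runs for 7 days, with ECGs predose and 1 hour postdose each day (Protocol Appendix 3). A reading above 500 ms on one day could be followed by the next dose with no numeric limit reached. In Part A each subject takes one dose, so a withdrawal rule cannot prevent another.

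**Working it through.** The plan gives no figure of its own here, so the check is the logic of the criterion.

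**Inputs.** Level 475 ms for both sexes; rise 60 ms for women and 40 ms for men (Protocol 6.21.1). Highest QTcF at entry 470 ms for women and 450 ms for men (Protocol 4.3, Exclusion 5). Let b be the reference QTcF, taken to be an ECG that met the entry limit.

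**Formula.** The criterion is met when QTcF > 475 and QTcF − b > d. The highest QTcF that does not meet it is max(475, b + d).

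| b (ms) | Women, d = 60 | Above 500 by | Men, d = 40 |
|---|---|---|---|
| 415 | 475 | – | 475 |
| 430 | 490 | – | 475 |
| 440 | 500 | 0 | 480 |
| 441 | 501 | 1 | 481 |
| 450 | 510 | 10 | 490 |
| 460 | 520 | 20 | not admitted |
| 470 | 530 | 30 | not admitted |

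For women, b + 60 > 500 exactly when b > 440. The maximum is 470 + 60 = 530 ms, or 450 + 60 = 510 ms if entry is in practice held to the Appendix 4 normal range. For men the maximum is 450 + 40 = 490 ms, so the gap does not arise.

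**Effect of the reference ECG.** Take a constructed case: screening 420, Day 1 predose 445, postdose 503 ms. Against screening the rise is 503 − 420 = 83 ms and the criterion is met. Against Day 1 predose it is 503 − 445 = 58 ms and it is not.

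**How many women could be affected.** The documents do not say, so this part rests on assumptions: female QTcF normal with mean 410 to 420 and SD 15 to 20 ms, cut off at 470, and half of the 6 active subjects per cohort women. The share of admitted women with b > 440 is [Φ((470 − m)/s) − Φ((440 − m)/s)] / Φ((470 − m)/s):

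- m = 410, s = 15: 0.023
- m = 410, s = 20: 0.066
- m = 420, s = 15: 0.091
- m = 420, s = 20: 0.153

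Over three Part B cohorts (3 × 3 = 9 active women) that is 9 × 0.023 = 0.2 to 9 × 0.153 = 1.4 women. These women must also have a rise large enough to pass 500 ms but no more than 60 ms. With one reading each and a mean rise of 10 ms (SD 12), the chance of at least one such reading among the nine is 0.01% to 0.35%. At a mean rise of 20 ms (SD 12) it is 0.1% to 2.3%. If entry is held to 450 ms, these fall to about 0.001% to 0.009% and 0.02% to 0.14%.

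**With a cap.** The criterion plus a separate limit of 500 ms gives min(max(475, b + 60), 500) for women. This is unchanged up to b = 440 and 500 ms above that. The male values are unchanged.

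**The case against.** The strongest reply is that the numeric criterion is not the only protection. Protocol 6.10 states that "the PI or a designated physician will review each of the ECGs", and each is classed for clinical significance. Protocol 6.17 has AEs documented from "vital signs, ECGs, EEGs, or any other assessments that are relevant to subject safety". Protocol 6.17.9 says abnormal findings "should not be reported as AEs unless they are associated with clinical signs and symptoms", but also allows an AE when the finding leads to discontinuation or the investigator judges it medically important, so symptoms are not required. Such an AE opens the AE withdrawal ground in 6.21.1. In Protocol 6.20 the Grade 3 rule applies when toxicities "are observed in 2 or more subjects on active treatment in that dose group", but the next item can act on one subject with a related SAE or related significant AE. Part B subjects are inpatients throughout dosing.

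All of this stands. A reader might infer that a woman above 500 ms would simply go on being dosed, and the documents do not support that. What remains is that every one of these routes depends on judgment and none states a QTc number. The scheduled Part B committee review uses data through Day 8, after the last dose (Protocol 9.8.1). Protocol 6.20 adopts CTCAE version 5, but its QTc grades are not reproduced, and the CRC Plan and Study Safety Plan are not available, so a number could exist there.

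A reader might also infer that no ECG baseline is defined anywhere. That goes too far: SAP 5.2 defines one, and Protocol 8.1 leaves further definitions to the SAP. Only the link to the withdrawal rule is missing.

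Two further points are fair. A woman at 451 to 470 ms lies outside the Appendix 4 normal range, so she enters only if a physician does not consider the ECG clinically significant; 530 ms is the extreme case. And 500 ms as a stopping limit is a proposal, since the plan uses it only for reporting.

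**Conclusion.** The concern holds as a gap in a written safety rule. The 440 ms threshold and the 530 ms maximum (510 ms with entry at 450 or below) follow exactly from the text and need no distributional assumption, only that the reference ECG met the entry limit. The gap is specific to women and matters for repeat dosing in Part B.

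It should not be read as a sizeable risk. One can produce a large figure: with a mean rise of 30 ms (SD 15), entry up to 470 ms and the least favourable baseline distribution, the expected number of uncovered readings among nine women is 0.12. It falls to about 0.02 if entry is held to 450 ms. Nothing in the documents supports a rise of that size, and Protocol 3.2.1 bases dose selection on CNS and respiratory effects, with no QT signal mentioned. The event is unlikely. The case for changing the rule is that this is first-in-human dosing of healthy volunteers and the repair is small.

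**What to change.** Amend the ECG criterion in Protocol 6.21.1 in two ways:

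- Add, for either sex, *or QTcF >500 ms (mean of triplicate, confirmed on repeat)*.
- State that the increase is measured from the Day 1 predose triplicate mean, as defined in SAP 5.2.

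Triplicate ECGs are already taken at each time point (Protocol 6.10), so no new data are needed.

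The cost is a protocol amendment, which under Protocol 9.14 usually needs ethics committee approval if substantive. Human data already exist (Protocol 3.2.1), so the cap would apply to later cohorts only and should be described that way. The clinical downside is a rare extra withdrawal.
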